## Study Protocol

### I. Hypotheses and Specific Aims:

The primary objective of this randomized controlled trial is to determine efficacy of physical activity behavior-change telerehabilitation on improving physical activity after total knee arthroplasty (TKA).

**Aim 1:** To determine if PAB (Physical Activity Behavior-Change) intervention results in improved physical activity after TKA compared to the control group (CTL). Physical activity will be measured using accelerometer-based wearable sensors and self-reported daily activity (Life-Space Assessment).

**Hypothesis 1.1:** The PAB group will have greater increases in accelerometer-assessed daily step count (primary outcome) and percent time engaged in standing & walking activity than the CTL group from PREOP to POST2 (primary endpoint), and group differences will persist at POST3.

**Hypothesis 1.2:** The PAB group will have greater improvements in Life-Space Assessment scores than the CTL group from PREOP to POST2 (primary endpoint), and group differences will persist at POST3.

**Aim 2:** To determine if PAB intervention results in better physical function after TKA compared to the CTL group. Physical function will be measured with standardized performance-based (30-Second Chair-Stand Test, Timed Up-and-Go, Six-Minute Walk Test) and self-report (Western Ontario and McMaster Universities Osteoarthritis Index [WOMAC] and Veterans RAND 12-Item Health Survey [VR-12]) measures.

**Hypothesis 2:** The PAB group will have greater improvements in all functional outcomes compared to the CTL group at POST2 and POST3 test points, with outcomes meeting clinically meaningful thresholds.

**Exploratory Aim:** To identify predictors underlying responsiveness to PAB rehabilitation (i.e., change in average daily step count) from PREOP to POST2 in the PAB group.

**Hypothesis 3:** We expect preoperative daily step count and physical activity-related psychosocial factors (self-efficacy, stage of change, social support, fear of falling) will be significant determinants of intervention responsiveness, in addition to key demographic, anthropometric, and comorbidity determinants.

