## **B. Description of Population to be Enrolled:**

100 Veterans (50 per group) will be enrolled from Denver VAMC and the University of Colorado Hospital (UCH). Potential participants scheduled for TKA surgery will be identified by a VAMC or UCH surgeon who will refer candidates for study screening. Flyers will also be provided to orthopedic surgeons and health-care providers in the greater Denver metro area. Upon referral and prior to surgery, Veterans will be screened by a research team member, provide informed consent and participate in a pre-operative (PREOP) test session. Consent will be obtained face to face, or with an e-consent. The e-consent will be available to the participant prior to the consent discussion. A qualified study team member will Zoom phone/video call the potential participant. The potential participant will verify their identity. The study team member will explain the consent process and that the participant can navigate forward and backward through the consent form pages and that they may return to the form if later if they want time to think about their participation. The study team member will read the consent form with the participant and will answer all questions that the participant has. The participant and the study team member will both sign and date the consent form and the participant will be able to download or email themselves a copy of the signed form.

Physical activity at PREOP will be quantified as average daily step count (accelerometer-based monitors; see *Accelerometer-based Activity Monitoring* below). To ensure representative physical activity levels between groups, randomization will be stratified using two levels of PREOP step count: <5000 and ≥5000 steps/day. Randomization will also be stratified by decade of age. A research assistant, who is not involved in participant testing/intervention, will manage randomization and maintenance of intervention codes. The study will adhere to the CONSORT statement recommendations for reporting randomized trials (Figure 3).

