## **F. Data Analysis Plan:**

The primary outcome for this study is average number of steps taken per day, as measured by accelerometer-based wearable sensors (activPAL) over a 7-day period at the end of the intervention. This time point is chosen for clinical relevance to establish efficacy of the intervention. Sustainability will be tested as a secondary outcome, by assessing steps taken per day six months after conclusion of the intervention period. Other secondary outcomes include time spent in standing/walking activities and physical function measures. Preliminary descriptive and graphical analyses (including boxplots, scatterplots, profile plots of change over time) will be used for data cleaning, data visualization, and assessing statistical assumptions.

***Primary Analysis (Aim 1):*** The primary analysis will be an intent-to-treat comparison of the differences between the study groups (PAB and CTL) in the change average daily step count from PREOP to POST2 (primary endpoint). Statistical inference will be based on the estimated coefficient for the group variable using an analysis of covariance (ANCOVA) model with change in average daily step count from PREOP to POST2 as the response variable. Additional covariates include the stratification variables (PREOP physical activity and age) to improve the precision of the estimate. The conclusion about group differences will be made based on this single statistical test to control the type I error rate at 0.05. A similar between-group analysis will be performed on the change in daily step count from PREOP to POST3 (6-month effect post-intervention). A sensitivity analysis will be done to evaluate whether conclusions would differ when other covariates are added to the model (e.g., demographics, anthropometrics, comorbidities, psychosocial factors).

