***Secondary Analyses (Aims 1 & 2):*** Differences between study groups in the secondary outcomes of 1) time spent in standing/walking activity (activPAL) and 2) physical function (performance-based and self-reported outcomes), from PREOP to POST2 will be analyzed as described above for the primary analysis. All outcomes will also be analyzed at POST3 to evaluate the long-term sustainability of the PAB intervention. We anticipate that the secondary outcomes will be correlated with the primary outcome, and would interpret the results from the secondary analysis as reinforcing the findings in the primary outcome. Failure to observe consistency between primary and secondary outcomes will be interpreted as evidence that the effects of the PAB intervention are not clear, and that further study is necessary to resolve inconsistencies. This approach reduces the risk of false-positive conclusions resulting from multiple statistical tests.

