## Statistical Analysis Plan

An intention-to-treat approach was used for the primary data analysis. The two treatment arms were compared by demographics and baseline clinical characteristics using standardized mean difference and confidence intervals. Observed means of the primary and secondary outcomes were calculated. To assess group differences in the primary outcome (average daily step count), a linear mixed model (LMM) was used. The LMM accounted for the within-subject correlation associated with repeated measures through the inclusion of a random intercept for subject. Decade of participant age was included in the LMM as a continuous fixed effect. The model also included as fixed effects time and an interaction between intervention arm and time. Between-group difference at baseline was set at zero, so estimated baseline scores were equal between groups.

The primary analysis was conducted using the first 3 time points (pre-surgery, 8 weeks post-surgery, 14 weeks post-surgery), and the test of intervention effect on daily step count was tested using a Likelihood Ratio Test (LRT). P-values for the effect of intervention were derived from a LRT comparing the model with interaction of intervention arm and time versus the reduced model without the interaction. Contrasts were used to estimate group means and confidence intervals.

Secondary and exploratory analyses used the same methods as the primary outcome (pre-surgery, 8 weeks post-surgery, 14 weeks post-surgery, and 38 weeks post-surgery), and week 38). A secondary LMM analysis with the four time points was also conducted to test for group difference in daily step count at Week 38. All analyses were performed using R statistical software version 4.3.0.

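### The SAP's physical-function models keep age decade but drop preoperative step count, the other randomisation stratum, without a stated reason; the precision lost is small

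*Combined protocol and SAP*

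**What the plan says.** Protocol section IV.B sets the allocation: "randomization will be stratified using two levels of PREOP step count: <5000 and ≥5000 steps/day", and decade of age is the second stratification factor.

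Protocol section IV.F, Primary Analysis, sets the covariates: "Additional covariates include the stratification variables (PREOP physical activity and age) to improve the precision of the estimate". The Secondary Analyses paragraph carries this to Aim 2: "physical function (performance-based and self-reported outcomes), from PREOP to POST2 will be analyzed as described above for the primary analysis". The outcomes meant are defined under Aim 2: "Physical function will be measured with standardized performance-based (30-Second Chair-Stand Test, Timed Up-and-Go, Six-Minute Walk Test) and self-report" measures, the latter being WOMAC and VR-12.

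The SAP replaces the ANCOVA with a linear mixed model that has a random intercept and the baseline arm difference fixed at zero. On covariates it says "Decade of participant age was included in the LMM as a continuous fixed effect" and then "The model also included as fixed effects time and an interaction between intervention arm and time". For the other outcomes: "Secondary and exploratory analyses used the same methods as the primary outcome".

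**The concern.** Of the two variables that the protocol uses for stratification and names for adjustment, one survives in the SAP's list of fixed effects and the other does not. For daily step count nothing is lost, because PREOP steps is the first response in the repeated-measures vector. For a function outcome the vector holds only that outcome's own baseline, so PREOP steps does not enter at all.

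What is at stake is limited. Omitting a stratification variable does not bias the treatment estimate under randomisation. The cost is some precision on the Aim 2 outcomes and an unexplained departure from the protocol's covariate list and from the allocation scheme.

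The point does not cover daily steps. It makes no claim about standing and walking time, whose own baseline comes from the same sensor week. Life-Space is affected in the same way, but the protocol's secondary-analysis paragraph does not name it, so it is included only by extension.

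**Working it through.** **1. Terms, side by side**

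| | Age decade | PREOP steps | Outcome's own baseline |
|---|---|---|---|
| Randomisation (IV.B) | stratum | stratum | no |
| Protocol ANCOVA (IV.F), function | covariate | covariate | not stated as a covariate; the response is change from PREOP |
| SAP model, daily steps | covariate | in, as baseline response | the same variable |
| SAP model, function | covariate | absent | in, as baseline response |

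**2. The plan's own figure.** Section IV.B states 80.7% power for 40 per arm and d = 0.64. A noncentral-t calculation gives 80.70%, and 80/(1 − 0.20) = 100 enrolled, so both reproduce. They concern daily steps; no power or precision figure is given for function outcomes. The check below takes n = 80.

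**3. Assumptions.** The documents give no correlation between PREOP steps and function. I take r = 0.3 to 0.5, equal at all visits, and a within-subject correlation ρ of 0.5 to 0.7. Section IV.F says only "We anticipate that the secondary outcomes will be correlated with the primary outcome", which is indirect support. The share below 5000 steps comes from Table 1 (5623 ± 2230): Φ((5000 − 5623)/2230) = Φ(−0.279) = 0.390.

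**4. Reported standard error, closed form.** With outcome variance 1 and the baseline difference fixed at zero, the variance of the week-14 contrast is proportional to 1 − ρ². A PREOP-steps main effect takes r² out of the between-subject variance. That leaves total variance 1 − r² and correlation ρ′ = (ρ − r²)/(1 − r²). Hence

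SE ratio = √[(1 − r²)(1 − ρ′²)/(1 − ρ²)].

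- ρ = 0.6, r = 0.3: ρ′ = 0.51/0.91 = 0.560; √(0.91 × 0.686/0.64) = 0.988.
- ρ = 0.6, r = 0.5: ρ′ = 0.35/0.75 = 0.467; √(0.75 × 0.782/0.64) = 0.957.

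| ρ | r = 0.3 | r = 0.5 |
|---|---|---|
| 0.5 | 0.983 | 0.943 |
| 0.6 | 0.988 | 0.957 |
| 0.7 | 0.991 | 0.970 |

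The reported SE therefore falls by 0.9% to 5.7% over this grid.

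The ANCOVA form gives the same answer. The partial correlation of PREOP steps with later function, given baseline function, is p = r(1 − ρ)/√[(1 − ρ²)(1 − r²)]. At ρ = 0.6, r = 0.5 this is 0.20/√(0.64 × 0.75) = 0.289, and √(1 − 0.289²) = 0.957.

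**5. Simulation of the SAP-type model.** Settings: n = 80, no treatment effect, allocation balanced within step stratum by age decade (assumed decade shares 20/45/30/5%, no age effect), ρ = 0.6, 3 visits, 3,000 runs per case. Each SE is relative to the model without PREOP steps:

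| Added term | Reported SE, r = 0.3 / 0.5 | True (empirical) SE, r = 0.3 / 0.5 |
|---|---|---|
| Continuous PREOP steps | 0.988 / 0.958 | 0.995 / 0.972 |
| Two-level stratum | 0.993 / 0.977 | 1.000 / 0.995 |

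Four visits give nearly the same values (true SE 0.995 / 0.971 continuous, 1.000 / 0.994 stratum). In patients, 1/0.995² = 1.01 and 1/0.971² = 1.06. Over ρ = 0.5 to 0.7 the true gain with continuous steps is about 0.2% to 3.5%. An interaction of PREOP steps with time adds nothing (reported-SE ratios 0.990 / 0.960).

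The true gain is smaller than the reported one because stratified allocation has already balanced the coarse part of PREOP steps. Null rejection of the likelihood ratio test without the covariate was 4.3% to 5.5% (Monte Carlo SE 0.4 points), so no conservatism is detectable.

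**6. Daily steps.** Here PREOP steps is itself the baseline response. Adding it as a covariate raised null rejection from 5.9% to 8.3% with the stratum (reported/true SE 0.92) and to 13.4% with the continuous count (0.83).

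**The case against.** - **Another reading of the protocol.** In the primary analysis, PREOP physical activity is both a stratum and the baseline of the response. Analysing function in the same way could mean adjusting each outcome for its own baseline, which the SAP model already does. This reading is possible. Against it, the protocol calls the covariates stratification variables, and a function test's own baseline is not one.
- **The model changed wholesale.** A covariate list written for a change-score ANCOVA need not carry over term by term to a constrained-baseline mixed model. That is fair, and step 6 shows that carrying it into the daily-step model would do harm. It does not explain why age was kept and PREOP steps left out of the function models.
- **The stratum itself gains almost nothing.** This stands. Its true-SE gain is 0.6% or less, so the precision argument rests on the continuous count, a form the protocol does not clearly specify.
- **The correlations are weakly anchored.** This also stands. The protocol's remark about correlated outcomes concerns how results are read together, not PREOP steps against function. At lower values the gain vanishes. It would be larger if PREOP steps predicted later function more strongly than assumed here. At p = 0.4, above any value on this grid, omitting it raises the ANCOVA SE by 1/√(1 − 0.16) − 1 = 9.1%, and simulated null rejection falls to 3.9%. Nothing in the documents supports that case.

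**Conclusion.** The concern holds as a minor point. On the more natural reading of the protocol, PREOP step count should be a covariate for the physical-function outcomes; the SAP leaves it out and does not say why. There is no bias, no detectable distortion of the test under equal correlation across visits, and no effect on the primary conclusion. The protocol uses these outcomes only to reinforce the primary result.

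The fairest measure of the loss is the true standard error. With continuous PREOP steps it would fall by 0.5% to 2.9% at ρ = 0.6 and r = 0.3 to 0.5; with the stratum the gain is negligible. These sizes rest on assumed correlations. The omission itself rests only on the text.

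**What to change.** In the mixed models for chair stand, Timed Up-and-Go, six-minute walk, WOMAC and VR-12 (and Life-Space, if analysed the same way), add PREOP step count as one fixed effect. The continuous count is preferable because it carries nearly all the gain. The two-level stratum is acceptable if the aim is only to reflect the allocation. An interaction with time is optional.

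The SAP is written in the past tense. If the analyses are complete, report the adjusted model alongside the existing one and state in one sentence why the covariate was left out.

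Do not add PREOP steps to the daily step-count models at week 14 or week 38.

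The cost is a line of SAP text, one extra parameter per model and a rerun. Stratification requires the variable, so it is known for everyone randomised.

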#### *Data Collection and Outcomes*

Preoperative testing will occur 2 weeks prior to TKA (PREOP). Postoperative testing will occur midway through the PAB intervention (POST1), at the end of PAB intervention (POST2), and 24 weeks after PAB intervention (approximately 9-months after TKA) (POST3). The POST1 test will assess early between-group responses to intervention, while the POST2 test will assess group differences at intervention end (Primary End Point). The POST3 test is critical, as a key component to assessing success of behavior change is the long-term persistence of behavior change. Each test session will include the standardized procedures described in the next sections. Importantly, all test sessions occur at participant homes, to eliminate time and travel burdens for the participants and minimize barriers for rural participants. The 30-Second Chair Stand Test and Timed-up-and Go may be conducted remotely via video call and surveys may be conducted via phone/video call or through REDCap. Semi-structured interviews will occur following randomization, and again following the POST2 assessment period. Up to 20 participants will be randomly selected from the PAB group to have at least 10 participants participate in semi-structured interviews at both time points. An interview guide will be used with questions regarding the PAB program, perceptions of barriers and facilitators to physical activity, and perceptions of participation in everyday life. Depending on participant preference the interview can occur in-person, over the phone, or via an audio-visual application. All interviews will be audiorecorded and transcribed verbatim by a research team member or an approved transcription service.

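### The SAP's primary p-value tests the whole arm-by-time interaction over weeks 8 and 14, not the POST2 group difference that the protocol makes its single confirmatory test

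*Combined protocol and SAP*

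**What the plan says.** **Protocol, section F (Data Analysis Plan), Primary Analysis.** The quantity that carries inference is given thus: "estimated coefficient for the group variable using an analysis of covariance (ANCOVA) model with change in average daily step count from PREOP to POST2". That change is the outcome modelled. The decision rule follows: "The conclusion about group differences will be made based on this single statistical test to control the type I error rate at 0.05".

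**Protocol, section C, Data Collection and Outcomes.** The two visits during treatment have different roles. Of the earlier visit it says: "The POST1 test will assess early between-group responses to intervention". Of the later visit it says: "while the POST2 test will assess group differences at intervention end (Primary End Point"). Hypothesis 1.1 likewise concerns change "from PREOP to POST2 (primary endpoint), and group differences will persist at POST3".

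**Statistical Analysis Plan.** A random-intercept mixed model is fitted to pre-surgery, week 8 and week 14, with the baseline difference between arms fixed at zero. In the SAP's words, "the test of intervention effect on daily step count was tested using a Likelihood Ratio Test (LRT"). On the source of the p-value it adds: "P-values for the effect of intervention were derived from a LRT comparing the model with interaction of intervention arm and time"; the comparator is the model that omits this interaction. Contrasts are mentioned only as the source of group means and confidence intervals. The SAP does not say whether time is categorical or linear, and does not mention the ANCOVA.

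**The concern.** Both texts are current, and they attach the confirmatory conclusion to different null hypotheses. The protocol asks whether the arms differ at POST2. The SAP asks whether they differ at week 8, at week 14 or at both (categorical time), or whether their trajectories have different slopes (linear time). With the baseline difference set at zero and time categorical, the interaction terms are exactly the two arm effects at weeks 8 and 14, so dropping them tests both together.

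The trial has one claim with controlled type I error. Under the SAP that claim could be carried by POST1, which the protocol treats as an early look, while the week-14 interval includes zero. The reverse can also happen: a clear week-14 difference can be missed because the joint test spends a degree of freedom on week 8. A reader who has both documents cannot tell which p-value decides the trial.

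**Working it through.** **Inputs from the documents.** Protocol section B: d = 0.64, 40 evaluable per group, two-sided 5% t-test, 80.7% power. SAP: random intercept (equal correlation between visits), zero baseline difference, three visits.

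**Assumptions not in the documents.** Categorical time, complete data, between-visit correlation ρ = 0.5, 0.6 or 0.7, large-sample normality, and a range of week-8 effects.

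**1. Reproduce the planned power.** Non-centrality = 0.64 × √(40/2) = 2.862. A non-central t with 78 df gives 80.7%, as stated. The normal approximation gives 81.7%, which is the comparator below.

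**2. Joint distribution of the two arm effects.** Given baseline, each estimate has variance 2σ²(1 − ρ²)/n, and their covariance is 2σ²ρ(1 − ρ)/n. Their correlation is therefore r = ρ/(1 + ρ) = 0.333, 0.375, 0.412.

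**3. Scale to the plan.** Let the effects at weeks 8 and 14 be a and b times the effect that gives a z-mean of 2.862. Since 2.862² = 8.192, the LRT has 2 df, critical value 5.991, and non-centrality

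λ = 8.192 × (a² − 2rab + b²)/(1 − r²).

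Example with ρ = 0.5, a = 0.5, b = 1: λ = 8.192 × (0.25 − 0.333 + 1)/0.889 = 8.448, so LRT power is 74%. The week-14 contrast has 82%.

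**4. Results over ρ = 0.5 to 0.7** (joint rates from 1,000,000 draws per correlation):

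| Effect at week 8, week 14 (fraction of planned) | LRT significant | Week-14 contrast significant | LRT only | Contrast only |
|---|---|---|---|---|
| 0, 0 | 5% | 5% | 2.5% | 2.5% |
| 1, 1 (sustained) | 87–89% | 82% | 9–10% | 2–3% |
| 0.5, 1 (building) | 73–74% | 82% | 1–2% | 9–10% |
| 1, 0.5 (fading) | 73–74% | 30% | about 45% | 1% |
| 1, 0 (week 8 only) | 78–81% | 5% | 73–76% | 0.1% |
| 0.5, 0 (week 8 only, half size) | 26–27% | 5% | 22–23% | 1% |

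The LRT-only column is a significant primary p-value with a week-14 interval that includes zero.

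**5. Check by simulation** (1,500 trials per case, maximum likelihood fits, ρ = 0.5 and 0.7). The LRT rejected in 4.8% and 4.2% of trials with no effect, and in 78% and 81% with a full-size week-8-only effect. The week-14 contrast rejected in 5.2% and 5.7% of the latter.

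**6. Linear time.** If the interaction is linear in weeks (0, 8, 14), the LRT has 1 df and the week-8-only rejection rate falls to 11% and 8%. It is then a slope test, which is still not the protocol's POST2 coefficient.

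**The case against.** **Type I error is not inflated.** A reader might infer that it is. There is still one primary p-value, and it has about 5% size when neither visit shows an effect. This stands: the defect is which hypothesis is tested.

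**The worst figures need an effect that shrinks during treatment.** This is fair. The documents give no week-8 effect and do not settle the shape. By week 8, six or seven of the ten sessions have been held, which could favour an early peak. But the step target rises by 3% on the previous week. The protocol's earlier cohort was also well below pre-operative steps at month 1 (3598 against 5623) and near them at month 3 (5512). A building effect is at least as plausible. In that case the SAP's test is the stricter one and loses power, so the mismatch still matters.

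**A likelihood-based model is foreseen.** Protocol section E supports analysing all available data if they are missing at random, and a POST2 ANCOVA drops participants without POST2. This justifies the mixed model, but not a change of hypothesis: the same model yields a 1-df week-14 contrast.

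**Week 38.** A reader might infer that the week-38 p-value pools weeks 8, 14 and 38, because secondary analyses are said to follow the primary methods. The documents do not support that as a finding. The SAP states that the four-visit model tests the group difference at Week 38, and the sentence suggesting otherwise is garbled. For POST3 the protocol says: "A similar between-group analysis will be performed on the change in daily step count from PREOP to POST3". This is a wording query only.

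**Conclusion.** The mismatch is real and needs correcting. The SAP's primary p-value does not test the hypothesis on which the protocol stakes its conclusion, and no reason for the change is given.

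The size depends on the unknown week-8 effect. At the planned POST2 effect, the two tests reach different conclusions in about one trial in nine, whether the effect is sustained (9–10% plus 2–3%) or building (1–2% plus 9–10%). The direction differs: the LRT is the more lenient test in the first case and the stricter in the second. The large figures (about 45%, and 78–81%) apply only to fading or week-8-only effects.

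Two stronger readings are not supported: that the LRT would usually give a false claim, and that it always costs power. With equal effects at both visits it has more power (87–89% against 82%).

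All of these figures assume categorical time, complete data, 40 per arm and a correlation of 0.5 to 0.7. Under linear time the week-8-only rates are much lower.

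**What to change.** 1. Rest the confirmatory conclusion on the POST2 difference, using the prespecified ANCOVA of PREOP-to-POST2 change. The SAP is written in the past tense, so returning to the documented test avoids choosing a new one after the data.
2. Beside it, report the 1-df arm-by-week-14 contrast from the fitted mixed model with its p-value. This is the all-available-data analysis that protocol section E foresees, and it covers participants without POST2.
3. Keep the joint LRT as supportive, stating its time coding and degrees of freedom.
4. Disclose why the test departed from the protocol.
5. Confirm that the week-38 p-value is the arm-by-week-38 contrast of the four-visit model and not a pooled LRT.

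The cost is one ANCOVA fit, one contrast from a model already fitted, a paragraph of disclosure and one clarified sentence. The downside is less power than the joint test if the effect is equally large at week 8: about 82% against 87–89% for the week-14 test at the planned size.
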